5.5.4 Follow-up Visits

A follow-up visit will be performed at day 90 by phone in case of discharge. Patient data after the ICU discharge will be gathered through the patient medical file .

6 Adverse Event Reporting

6.1 Definitions

6.1.1 Adverse Event

This study uses posaconazole, which is an antifungal agent licensed for prophylaxis as well treatment of invasive fungal infections. The clinical indications and dosages used in this trial are similar to the licensed indications and dosages or lower; therefore no potential harmful risks are expected in this cohort. Furthermore, the study medication, posaconazole, given as antifungal prophylaxis, is given on top of standard intensive diagnostic work-up to detect a fungal infection as soon as possible.

We strongly believe the burden for the patient as well as the risk for severe adverse events is reduced to an absolute minimum. The risk-classification is assessed as negligible to the patient population receiving study drug at the current regimens.

An Adverse Event (AE) is any untoward medical occurrence in a patient or subject during an experiment, and which does not necessarily have a causal relationship with this treatment.

An AE can therefore be any unfavourable and unintended sign (including an abnormal laboratory finding), symptom or disease temporally associated with the use of a product, whether or not considered related to the product. Any worsening (i.e., any clinically significant adverse change in the frequency or intensity of a pre-existing condition) should be considered an AE.

The following AEs should be reported:

- New ALAT elevation after the start of posaconazole to >10 x ULN, not being explained by another overt reason
- QTc interval prolongation (QTc > 500 msec)

These adverse events are monitored as a part of SOC on ICU.

6.1.2 Serious Adverse Event

A Serious Adverse Event (SAE) is any untoward medical occurrence that results in any of the following:

- Death
- A life-threatening^a experience
- In-patient hospitalisation or prolongation of existing hospitalisation
- A persistent or significant disability or incapacity
- A congenital anomaly or birth defect
- Important medical events that may be considered an SAE when - based on appropriate medical judgement - they may jeopardise the subject and may require medical or surgical intervention to prevent one of the above outcomes

^aThe term "life threatening" in the definition of SAE refers to an event in which the subject was at risk of death at the time of the event. It does not refer to an event which hypothetically might have caused death if it was more severe.

6.1.3 Adverse Events of Special Interest

The following events should be reported within the same timelines as SAEs:

- Overdose
- Misuse/abuse
- Medication error

6.2 Adverse Events that do not require Reporting

In general, the following should not be reported as AEs:

- Pre-existing conditions, including those found as a result of screening (these should be reported as medical history or concomitant illness).
- Pre-planned procedures unless the condition for which the procedure was planned has worsened from the first trial-related activity after the subject has signed the informed consent.

Adverse events other than the above mentioned AE that should be reported, will be reported at the discretion of the treating physician.

Although these events should not be reported to the sponsor, these should be recorded in the patient's medical notes according to routine practice.

The following events not to be considered as SAEs are hospitalisations for :

- Pre-planned hospitalisation unless the condition for which the hospitalisation was planned has worsened from the first trial-related activity after the subject has signed the informed consent.
- A standard procedure for protocol therapy administration. However, hospitalisation or prolonged hospitalisation for a complication of therapy administration will be reported as an SAE.
- Hospitalisation or prolongation of hospitalisation for technical, practical, or social reasons, in absence of an AE.

6.3 Recording and Reporting of Averse Events

Investigators will seek information on AE at each patient contact. All events, whether reported by the patient or noted by trial personnel, will be recorded in the patient's medical record and in the (e)CRF within a reasonable time after becoming aware. If available, the diagnosis should be reported on the AE page, rather than the individual signs or symptoms. If no diagnosis is available, the investigator should record each sign and symptom as individual AEs using separate AE forms.

6.3.1 Assessment

All AEs must be evaluated by an Investigator as to:

- **Seriousness:** whether the AE is an SAE. See above for the seriousness criteria.
- **Severity:**

- If applicable: grading must be evaluated by an Investigator according to the current active minor version fo the National Cancer Institute (NCI) Common Terminology Criteria for Adverse Events (CTCAE, version 4.0) **OR**
- If applicable: severity must be evaluated by an Investigator according to the following definitions:
 - Mild – no or transient symptoms, no interference with the subject's daily activities
 - Moderate – marked symptoms, moderate interference with the subject's daily activities
 - Severe – considerable interference with the subject's daily activities, unacceptable

- **Causality:**
 - None – An AE which is not related to the trial product or experiment
 - Unlikely – An AE for which an alternative explanation is more likely (e.g. concomitant medication(s), concomitant disease(s)), and/or the relationship in time suggests that a causal relationship is unlikely
 - Possible – An AE which might be due to the use of the trial product or the experiment. An alternative explanation is inconclusive. The relationship in time is reasonable; therefore the causal relationship cannot be ruled out.
 - Probable - An AE which might be due to the use of the trial product or the experiment. The relationship in time is suggestive (e.g. confirmed by dechallenge). An alternative explanation is less likely.
 - Definitely – An AE which is listed as a possible adverse reaction and cannot be reasonably explained by an alternative explanation. The relationship in time is very suggestive (e.g. it is confirmed by dechallenge and rechallenge).

6.3.2 Timelines for reporting

- After informed consent has been obtained but prior to initiation of trial treatment, only serious adverse events caused by a protocol-mandated intervention (e.g.) should be reported
- After initiation of trial treatment, adverse events will be reported as follows:
 - All adverse events will be reported during study treatment
 - Serious adverse events and adverse events of special interest will continue to be reported until 90 days

All SAEs/AESI as defined in the protocol must be reported to the Sponsor within 24 hours of the research staff becoming aware of the event.

Describe here the details of how the SAE must be reported by the Investigator to the Sponsor:

- By completing the SAE form in the (e)CRF

If an authorised Investigator from the reporting site is unavailable, initial reports without causality and expectedness assessment should be submitted to the Sponsor by a healthcare professional within 24 hours of becoming aware of the SAE, but must be followed-up by medical assessment as soon as possible thereafter.

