b: On NS, BA or BAL within the last 7 days before ICU admission or within 2 days after ICU admission; or based on a positive rapid test if PCR not available

c: BAL GM, BAL culture and serum GM within 48h after influenza diagnosis to collect mycological evidence for IAA-infection

d: BAL GM, BAL culture and serum GM between day 2 after randomization and ICU discharge, at the discretion of the treating physician, or later during ICU admission in case of clinical respiratory deterioration

e: Provided by either (A) a positive culture of *Aspergillus* cultured from BAL, (B) ≥2 positive cultures of *Aspergillus* cultured from a sputum or a bronchial aspirate or (C) a galactomannan (GM) optical density of ≥1 in BAL or ≥0.5 in serum

f: Study drug related adverse events

I Background and Rationale

Invasive aspergillosis has been regarded as an infectious complication of specific immunocompromised patients, which affects a relatively small group of patients. However, in recent years aspergillus disease has become a prominent problem in ICU-patients.

Influenza-associated aspergillosis (IAA) was recently found to be a frequent and severe complication of influenza pneumonia in critically-ill patients.[1] A retrospective observational study during the 2015/2016 influenza season indicated that among 144 patients admitted to the ICUs of all eight Dutch University Medical Centres with influenza, 23 (16%) developed IAA.[2] The underlying diseases in these patients were diverse, and 7 patients had been previously healthy. A 61% mortality rate was observed, including 5 of 7 previously healthy patients who died.[2] It is thus clear that IAA is an early and frequent complication of severe influenza pneumonia, and that delay in diagnosis and treatment increases the probability of death in these critically ill patients. Early diagnosis is difficult due to unspecific clinical and radiological presentation. [1,2]

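### Adverse-event reporting windows and the ALAT event are tied to posaconazole, so standard-of-care patients have no defined start for reporting and no defined end for non-serious events

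*Combined protocol and SAP*

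**What the plan says.** Section 6.3.2 sets two reporting states.

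- Before treatment: "After informed consent has been obtained but prior to initiation of trial treatment, only serious adverse events caused by a protocol-mandated intervention" are reportable.
- From treatment onward: "After initiation of trial treatment, adverse events will be reported as follows". Two rules follow: "All adverse events will be reported during study treatment", and "Serious adverse events and adverse events of special interest will continue to be reported until 90 days". The second does not say from when the 90 days run.

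Section 6.1.1 names two events that must be reported. One is "New ALAT elevation after the start of posaconazole to >10 x ULN, not being explained by another overt reason". The other is a QTc above 500 msec, whose definition does not mention posaconazole. The section adds: "These adverse events are monitored as a part of SOC on ICU".

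In the trial flowchart, footnote f limits the adverse-event row to "Study drug related adverse events". The serious adverse event row and the survival row carry no such footnote.

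The synopsis gives no active comparator, only SOC, and 2.4 describes a non-blinded trial. Section 3.1 gives posaconazole to the prophylaxis group only.

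**The concern.** Every time limit in 6.3.2 is expressed through an event, the start or the course of trial treatment, that happens in one arm only. A site that follows 6.3.2 literally would keep SOC patients under the pre-treatment rule throughout, while reporting all adverse events from posaconazole patients.

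Raised liver enzymes, QTc prolongation and serious complications can occur in critically ill patients without the drug. A concurrent randomised control is the natural means of separating such background events from drug effects. Section 1 states that posaconazole is not licensed for prophylaxis in this population, so the control has real value for safety. If events are collected under different rules, a difference in reported counts may reflect the rules and not the drug. Because staff know the allocation, nothing in the design would even out the reporting.

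**Working it through.** There is no planned figure to reproduce. The check sets the safety rules against the design, arm by arm.

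| Rule and place | Posaconazole arm | SOC arm |
|---|---|---|
| Start of reporting (6.3.2) | First dose, day 1 (3.1) | No date can be assigned |
| Pre-treatment rule (6.3.2) | Consent to first dose | Read literally, all of follow-up |
| End of non-serious reporting (6.3.2) | End of treatment | Not defined |
| End of serious and special-interest reporting (6.3.2) | 90 days, origin not stated | 90 days, origin not stated, from a window that never opened |
| ALAT event (6.1.1) | Can be met | Cannot be met |
| QTc event (6.1.1) | Can be met | Can be met; timing still falls under 6.3.2 |
| Adverse-event row, footnote f | Applies | Cannot apply |
| General recording (6.3) | Every contact, all events | Every contact, all events |
| Death reports (6.4) and 30- and 90-day mortality (5.5.2) | All subjects | All subjects |

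1. *Does an SOC patient have a treatment to initiate?* Not under the synopsis, 2.4 or 3.1. Sections 3.2 and 7.2 do mention a placebo, which would supply a start date. That wording contradicts the non-blinded SOC design, so it cannot be relied on for a window and is itself in need of correction.

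2. *Does other text give SOC patients a window?* Section 6.3 calls for recording at each contact but sets no start, no end and no rule for either arm. Section 6.2 leaves events outside the listed ones to the treating physician's discretion. Section 6.4 requires serious events to be sent within 24 hours, but allows exceptions by reference back to the protocol. None of these sets the missing dates.

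3. *Do the rules agree with one another?* No. Footnote f covers drug-related events, 6.2 makes unlisted events discretionary, 6.3 covers all events, and 6.3.2 covers all events during treatment. Nothing states which prevails, so two sites could both comply and still collect different SOC data.

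4. *How many patients are affected?* Under 7.1, 55 of 110, and 55/110 = 50%. Under the synopsis, 50 of 100, also 50%.

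5. *What stays comparable?* Mortality, because 5.5.2 times it from randomisation in both arms. So do the measured ALAT and QTc values, because 6.1.1 describes them as routine ICU monitoring. What is not comparable as written is the set of *reported* ALAT events, non-serious adverse events and non-fatal serious adverse events.

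6. *Is there an arm-neutral origin to use?* Yes: 5.5.2 defines day 1 as the day of randomisation.

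**The case against.** The strongest reply is that the gap is one of wording. Section 6.3 has investigators ask about adverse events at every contact and record all of them in the eCRF, with no limit by arm. It governs recording, while 6.3.2 governs reporting. The definition of a serious adverse event in 6.1.2 is arm-neutral, footnote f attaches only to the adverse-event row, and the QTc item does not depend on the drug. Safety is not among the objectives or endpoints, 7.2 describes no between-arm adverse-event analysis, and 6.1.1 argues that the risk is negligible, so limited reporting may be a deliberate choice.

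Much of this stands. A reader might infer that SOC patients have no safety capture at all, or that the arms cannot be compared on safety. The documents do not support either reading: 6.3 applies to both arms, deaths are reported for every subject, mortality is counted from randomisation, and the laboratory and ECG data should exist in both arms.

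The reply does not remove the core. Deliberately light reporting would still need the same start and end in both arms. An unresolved conflict between 6.3 and 6.3.2 is not a rule that sites can apply consistently. The absence of a planned between-arm analysis means that the harm falls on an expected comparison and not on a stated one; it does not make the collection even.

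**Conclusion.** The point holds in a limited form. For SOC patients, 6.3.2 gives no start for adverse-event and serious-adverse-event reporting and no end for non-serious reporting, and the ALAT item and footnote f cannot apply to them. Reported ALAT events, non-serious adverse events and non-fatal serious adverse events are therefore not collected on the same basis in the two arms.

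The defect covers one whole arm, half of the randomised patients. A reader might want to turn it into a number by assuming a background event rate and no SOC reports. The documents give no such rate, 6.3 argues against zero recording, the ALAT definition already excludes otherwise explained elevations, and no test of these events is planned. The size of the distortion is therefore unknown.

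The conclusion rests on two assumptions: that the SOC arm receives no placebo, as the synopsis, 2.4 and 3.1 indicate; and that sites may treat 6.3.2, the specific timing rule, as governing. The change should be made, but the trial's efficacy and mortality comparisons do not depend on it.

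**What to change.** 1. In 6.3.2, start adverse-event, serious-adverse-event and special-interest reporting at Day 1 (randomisation) in both arms. Give non-serious events one calendar window, stated in days and identical in both arms, so that it does not depend on when a patient stops the drug. State that serious and special-interest reporting runs to day 90 after randomisation.
2. In 6.1.1, re-anchor the ALAT item to elevation after randomisation. Keep the rest of the definition. If the clause excluding elevations with another overt explanation is to change, say so explicitly, because that alters the event and not just its time origin.
3. Reconcile footnote f with 6.2, 6.3 and 6.3.2, and state which events are recorded and reported, in both arms.
4. Correct the placebo wording in 3.2 and 7.2 so that it agrees with the non-blinded SOC design.
5. In 7.2, add a table by arm, for all randomised patients, of measured ALAT above 10 x ULN, QTc above 500 msec, and serious adverse events. The measured values do not rely on an unblinded judgement of cause.

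The cost is protocol and eCRF wording and more serious-event entries from the SOC arm. No new tests are needed, since ALAT and QTc are already followed in routine care. Differences in discretionary reporting under open-label conditions will be reduced but not removed.

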As influenza virus infection leads to lysis of infected cells, we believe that a severe influenza infection causes cytopathology of the epithelial lining of the trachea and bronchi, providing *A. fumigatus* the opportunity for invasive growth. Many patients developed invasive *Aspergillus* tracheobronchitis, which is a manifestation of invasive aspergillosis that is difficult to diagnose due to lack of specific radiologic features.[3] Furthermore, influenza may contribute to a hyperinflammatory status known as macrophage activation syndrome that contributes to pulmonary damage.[4] Disruption of anatomical barriers and the dysregulated host defense provides an opportunity for *A. fumigatus* to cause fulminant invasive disease. Although biomarkers, such as galactomannan, in BAL and serum are useful tools in diagnosing IAA, early diagnosis proved difficult in the above-mentioned Dutch observational study. Moreover, the median time to initiation of antifungal therapy after influenza diagnosis in survivors and non-survivors was two days versus nine days ($P<0.06$), which underscores that early intervention is critical for survival. Finally, a high azole resistance rate of 29% was observed in these Dutch ICUs, which further complicates patient management.[2,5]

Therefore we propose to perform **an interventional non-blinded randomized controlled multicentric Dutch-Belgian proof-of-concept interventional study** in patients with severe influenza admitted to the ICU, randomizing patients either to oseltamivir therapy with standard care for diagnosis and treatment of secondary infectious complications or to oseltamivir plus posaconazole prophylaxis.

Currently there is no mold-active antifungal agent licensed for prophylaxis of invasive mold disease in ICU patients. The antifungal azole posaconazole is the drug of choice for antifungal prophylaxis in neutropenic patients with acute myeloid leukemia and those with graft-versus host disease following allogeneic HSCT.[6,7] These studies showed that posaconazole prophylaxis reduced the prevalence of invasive aspergillosis to below 2% in these high risk patients. Posaconazole is however not licensed for prophylaxis in other patient groups, i.e. critically ill patients. Based on the experience in patients with hematological

malignancy we anticipate that posaconazole prophylaxis will be effective to reduce the IAA incidence and eventually outcome in patients at risk for IAA.

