6.4 Reporting requirements to Ethics Committee's and Health Authorities

The investigator is responsible for ensuring that all safety events are recorded in the (e)CRF and reported to the Sponsor in accordance with instructions provided below:

Who reports	What	To	Within which period
Investigator	AE	(e)CRF	Cfr protocol

Investigator	SAE (including death) AESI Pregnancy	Coordinating Investigator / sponsor	Immediately (within 24 hours of becoming aware of the event) Exceptions: cfr protocol
PI / sponsor	Each death of a subject from a Belgian site	Central EC	Immediately
PI (Belgian site)	Each death of a subject from an external Belgian site	Local EC	Immediately
PI (non- Belgian site)	Each death of a subject from an external non-Belgian site	According to local legislation	According to local legislation
PI / sponsor	Any SUSAR that is fatal or life- threatening	- Competent Authorities - All other member states if applicable - EC - Investigators - Marketing Authorisation Holder if applicable	Within 7 calendar days, every additional information within additional 8 calendar days
PI / sponsor	All other SUSAR's		Within 15 calendar days
PI / sponsor	Report of all SAE's	Competent Authorities	Annually or final report
		All other member states if applicable	Annually or final report
		EC	Annually a summary of the past year with a safety analysis and risk-benefit evaluation

The Sponsor will promptly evaluate all serious adverse events and adverse events of special interest against experience to identify and expeditiously communicate possible new safety findings to investigators, ECs and applicable health authorities based on applicable legislation.

7 Statistics and Data Analysis

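### Three incompatible rules govern which non-serious adverse events are collected, and the collection window is undefined in the standard-of-care arm

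*Combined protocol and SAP*

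**What the plan says.** Six places in the protocol bear on which AEs are collected.

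- Section 6.3.2 (timelines): "All adverse events will be reported during study treatment". This stands under a lead-in that starts the clock when trial treatment begins.
- Section 6.3 (recording): "All events, whether reported by the patient or noted by trial personnel, will be recorded" in the medical record and in the (e)CRF.
- Section 6.4 (reporting requirements): "The investigator is responsible for ensuring that all safety events are recorded in the (e)CRF and reported to the Sponsor". Its table gives the (e)CRF as the destination for AEs.
- Section 6.1.1 (definitions): "The following AEs should be reported", followed by two items. One is a new ALAT rise above 10 x ULN, timed from the start of posaconazole and without another evident explanation. The other is QTc above 500 msec.
- Section 6.2 (events not requiring reporting): "Adverse events other than the above mentioned AE that should be reported, will be reported at the discretion of the treating physician". The next sentence keeps certain events away from the sponsor and in the medical notes, but does not make clear which events it means.
- Trial flowchart, footnote f to the AE assessment row: "Study drug related adverse events".

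Section 6.1.1 also says "The clinical indications and dosages used in this trial are similar to the licensed indications and dosages or lower". The background section says "Posaconazole is however not licensed for prophylaxis in other patient groups, i.e. critically ill patients".

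**The concern.** Two sites that each follow the protocol can build different safety data sets, depending on which section their staff read. Section 2.4 describes the trial as non-blinded and multicentre, so a physician who exercises discretion or judges drug-relatedness knows the patient's arm. A physician watching for posaconazole toxicity may reasonably report more readily in that arm. A rule restricted to drug-related events could leave the SOC arm with nothing to report.

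What is at stake is any statement about how well critically ill patients tolerate posaconazole prophylaxis. The protocol itself describes this use as unlicensed. If the two arms are not collected under the same rule, a difference in non-serious AEs cannot be separated from a difference in reporting, and neither can an absence of difference.

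**Working it through.** The plan gives no figure on this point, so the check is a comparison of texts. I grouped the six places by the rule they set and then ran test events through each rule.

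**Grouping**

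- Rule A, everything: sections 6.3, 6.3.2 and 6.4.
- Rule B, two named events with the rest discretionary: sections 6.1.1 and 6.2. Section 6.2 refers back to the named events, so the two sections make one rule.
- Rule C, drug-related only: flowchart footnote f.

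**Test events (all non-serious)**

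| Event | Rule A | Rule B | Rule C |
|---|---|---|---|
| Posaconazole patient on treatment; not a named event; judged unrelated | Mandatory | Optional | Out of scope |
| Posaconazole patient on treatment; nausea, judged possibly related | Mandatory | Optional | In scope |
| SOC patient; not a named event | Recorded under 6.3; no window under 6.3.2 | Optional | Cannot qualify |
| SOC patient; ALAT above 10 x ULN | Recorded under 6.3; no window under 6.3.2 | Not covered as worded, because it is timed from the start of posaconazole | Cannot qualify |

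The first row is enough to show the conflict: one event gets three answers. The second row matters because section 3.3 itself lists nausea among the common AEs related to posaconazole, yet Rule B leaves its reporting to discretion.

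**Does any section resolve the conflict?**

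- No section states an order of precedence.
- Separating recording from reporting does not help. Section 6.3 sends every event to the (e)CRF, and the 6.4 table makes the (e)CRF the reporting route for AEs.
- Section 6.3.1 requires a causality grade for every AE, and its scale includes grades for events that are not related or unlikely to be related. Those grades would have little use if only drug-related events were collected, so footnote f does not fit 6.3.1 either.

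**The SOC arm**

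The synopsis gives no active comparator, only SOC. Three elements then have no defined meaning for an SOC patient: the on-treatment period in 6.3.2, the start of posaconazole in 6.1.1, and drug-relatedness in footnote f. Sections 3.2 and 7.2 mention placebo in passing, but the title, the synopsis and section 2.4 describe a non-blinded comparison with SOC. I have assumed that no placebo is given.

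**The case against.** The strongest reply is that the protocol intends a light safety regime for a marketed drug, that the events that matter most are covered by a clear rule, and that little hangs on the rest. Much of this stands. SAEs and AESIs go to the sponsor within 24 hours and are reported until 90 days, and the conflict over scope does not reach them. AEs are not among the primary or secondary endpoints in sections 2.2 and 2.3, and section 7.2 specifies no AE comparison. A light regime is a legitimate choice, but the protocol would have to state it once and apply it to both arms.

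A reader might infer several stronger points that the documents do not support.

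- *That there are four conflicting rules.* Sections 6.1.1 and 6.2 read naturally as one, so there are three.
- *That section 6.2 bars all other AEs from reaching the sponsor.* The sentence may refer only to pre-existing conditions and pre-planned procedures, or to events the physician chose not to report. The discretion sentence conflicts with 6.3.2 on any of these readings.
- *That the two-event list rests on the licensing sentence.* Section 6.1.1 uses that sentence to support its risk classification and does not give it as the reason for the list. Calling the indication similar to a licensed one sits badly with the background section, but that is a separate point.
- *That AE counts will be biased, or by a given amount.* The documents do not say how physicians will use their discretion. Any figure would only restate an assumed reporting gap.

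**Conclusion.** The inconsistency is real and should be corrected. Three rules on the scope of non-serious AE collection cannot all be followed, none is given precedence, and the timing and relatedness terms do not carry over to the SOC arm. Non-serious AE counts could therefore differ by arm, site and physician without any difference in true incidence. That consequence is an inference from the non-blinded, multicentre design and from physician discretion; the documents do not state it. It also assumes that the SOC arm receives no study drug.

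No size can be put on the effect, because the documents give neither expected AE rates nor reporting shares. The damage is confined to the interpretation of non-serious safety data. The primary test of IAA incidence and the scope of SAE and AESI reporting are untouched.

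**What to change.** Reconcile flowchart footnote f with sections 6.1.1, 6.2, 6.3, 6.3.2 and 6.4 so that all six state one collection rule for non-serious AEs. The rule should:

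- be the same in both arms;
- not depend on causality or on the treating physician's discretion (causality is graded after collection, as 6.3.1 already provides);
- use a calendar window counted from randomisation, so that it applies equally to SOC patients;
- time the ALAT item from randomisation as well, if that item is kept.

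Whether the scope is all AEs or a closed list is for the sponsor to choose. A closed list taken from routine ICU measurements would keep the workload small, but the all-event wording in 6.3, 6.3.2 and 6.4 would then have to be narrowed to match. Section 6.2 should also say exactly which events stay in the medical notes only. The SAE and AESI line in 6.3.2 stands under the same treatment-start lead-in, so stating the start from randomisation there too would be a useful tidying step.

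The cost is protocol and (e)CRF wording, plus some extra data entry if the broad scope is chosen.

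Separately, reconcile the sentence in 6.1.1 on similarity to the licensed indications with the background section's statement on licensing in critically ill patients, so that the risk classification does not rest on a disputed premise.
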